### **12.7.3 Exploratory Efficacy Endpoints**

The exploratory endpoints to further characterize the efficacy of tapinarof cream, 1% compared with vehicle control over time are:

- Time (days) to achieving a PGA treatment response, defined as days from date of first dose until achieving a PGA score of 0 or 1 with a minimum 2-grade improvement from Baseline. Subjects who have no PGA response will be censored at the date of their last PGA assessment.
- Proportion of subjects with a PGA score of 0 or 1 at Weeks 2, 4, and 8
- Proportion of subjects who achieve a PGA treatment response at Weeks 2, 4, and 8
- Mean absolute and percent change in PASI score from Baseline to Weeks 2, 4, 8, and 12
- Proportion of subjects with  $\geq 50\%$  improvement in PASI score (PASI-50) from Baseline to Weeks 2, 4, 8, and 12
- Proportion of subjects with  $\geq 75\%$  improvement in PASI score (PASI-75) from Baseline to weeks 2, 4, and 8
- Proportion of subjects with  $\geq 90\%$  improvement in PASI score (PASI-90) from Baseline to weeks 2, 4, and 8
- Mean change in %BSA affected from Baseline to Weeks 2, 4, and 8
- Mean % change in %BSA affected from Baseline to Weeks 2, 4, 8, and 12.

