7.4. Follow-Up Visit 7; Week 16 (Day 113 ±4 Days)

Subjects who do not enroll in the open-label long-term study will return to the study site at Week 16 to complete follow-up assessments as follows:

- Urine pregnancy test (females of child-bearing potential)
- Brief physical examination
- Vital signs measurement
- Blood sample collection for clinical laboratory tests
- Urinalysis
- PGA score
- %BSA affected calculation (performed before PASI)
- PASI
- LTS
- DLQI
- SF-36
- PSD
- Peak Pruritus-NRS
- AE recording
- Concomitant medication recording

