## 7. SAMPLE SIZE DETERMINATION

It is assumed that the proportion of subjects who achieve PGA score of clear (0) or almost clear (1) with a minimum 2-grade improvement from Baseline at Week 12 will be 40% for subjects receiving tapinarof compared with 15% for subjects receiving vehicle control. With 500 subjects randomized in a 2:1 ratio (approximately 333 subjects receiving tapinarof cream, 1% and approximately 167 subjects receiving vehicle cream) there will be > 99% power for statistical significance (2-sided  $p < 0.05$ ). If tapinarof response rate is 35%, and vehicle response rate is 20%, the power will be > 94%. Power comes from a Fisher Exact sample size calculation which is conservative. It is assumed that up to 25% of the subjects will be lost to follow-up by 12 weeks. These subjects will be included in the primary analysis in the ITT population using the multiple imputation method as detailed below.

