## **11. DATA CONVENTIONS FOR ANALYSIS**

### **11.1 General Statistical Principles**

All statistical tests will be performed at the 0.05 (two-sided) level of significance.

All observed and derived variables (e.g., change from baseline, percentage change from baseline, and response status) that are analyzed or summarized will be listed by subject. Descriptive statistics will provide an overview of the efficacy and safety results. For categorical parameters, the number and percentage of subjects in each category will be presented. The denominator for percentage will be appropriate for the purpose of the analysis. For continuous parameters, descriptive statistics will include number of subjects, mean, standard deviation (SD), median, minimum, and maximum.

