### **12.8.2 Secondary and Exploratory Efficacy Analyses**

The same methods as discussed for the primary analyses will be used to analyze all dichotomized and continuous secondary endpoints. The secondary efficacy endpoints will be tested sequentially in the order listed. Testing will stop if non-significance (2-sided  $p \geq 0.05$ ) is observed as described in Section 11.6.

Other exploratory efficacy endpoints will be analyzed using CMH test for proportions, and analysis of covariance (ANCOVA) model for continuous variables. CMH tests will be stratified by baseline PGA score, and ANCOVA models will include baseline PGA score as a covariate (2, 3 or 4), and baseline value of the endpoint as a continuous covariate. For proportions, the same MI approach describe above will be taken to deal with missing data. For continuous variables, the standard MI procedures for ANCOVA will be followed. Least squared means of treatment difference (tapinarof – placebo) along with the 95% CI will be reported.

Time to achieving a PGA success will be analyzed with the Kaplan Meier method in the ITT population based on Observed Cases. Treatment groups will be compared using a log-rank test. Estimates of median time to response from Kaplan Meier distribution will be computed. A Kaplan-Meier figure will also be generated.

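### Time to PGA response has no Week 12 cut-off, so read literally its Kaplan-Meier tail, and possibly the tapinarof median, rests on a small off-treatment group seen at Week 16

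*SAP*

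**What the plan says.** SAP 12.7.3 defines the time from first dose until a PGA of 0 or 1 with at least a 2-grade improvement, and sets no last visit. For the rest: "Subjects who have no PGA response will be censored at the date of their last PGA assessment". SAP 12.8.2 analyses this by Kaplan-Meier in the ITT population on observed cases, with a log-rank test and a figure, and adds: "Estimates of median time to response from Kaplan Meier distribution will be computed".

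PGA is on the Week 16 list in Protocol Table 1 and Protocol 7.4. On who attends, Protocol 7.4 says: "Subjects who do not enroll in the open-label long-term study will return to the study site at Week 16". Footnote a of Table 1 names three groups: premature withdrawals, subjects who fail to qualify for the long-term study, and subjects who qualify but decline. SAP section 3 places the visit about 4 weeks after the end of treatment.

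**The concern.** The rule gives subjects different lengths of follow-up according to what they do after Week 12. A non-responder who rolls over leaves the risk set at about Day 85. A non-responder who does not roll over stays in it, off study drug, until about Day 113, and a first response there counts as an event. Entry to that late group depends on choice, eligibility or early withdrawal, so it need not represent the randomized arm.

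Each event in a small risk set makes a large step in a Kaplan-Meier curve. If the tapinarof curve ends Week 12 a little above 0.5, a few such events would produce a reported median of about 16 weeks in a trial with 12 weeks of treatment. What is at stake is how one exploratory result is described.

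**Working it through.** **The plan's own figures.** SAP section 7 gives no event count, expected median or roll-over rate for this endpoint. Its power figures for the primary endpoint (333 v 167, two-sided 0.05) can be reproduced. For 40% v 15%, power exceeds 99.9% (stated: above 99%). For 35% v 20% it is 94.5% by pooled z and 93.8% by exact Fisher enumeration (stated: above 94%). The point does not depend on them.

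**Inputs from SAP section 7**
- Response at Week 12 "will be 40% for subjects receiving tapinarof compared with 15% for subjects receiving vehicle control"; the alternative case is 35% v 20%.
- Arms: "approximately 333 subjects receiving tapinarof cream, 1% and approximately 167 subjects receiving vehicle cream".
- Dropout: "It is assumed that up to 25% of the subjects will be lost to follow-up by 12 weeks".

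**Assumed, not in the documents:** 90% roll-over (range 60% to 95%), a Week 16 first-response rate of 2% to 20%, and cumulative response by Week 12 equal to the planned Week 12 rate. The true cumulative rate may be somewhat higher, because any earlier response counts.

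**Step 1. Size of the late risk set (tapinarof).** On study at Week 12: 333 × 0.75 ≈ 250.
- 40% response: 250 × 0.60 = 150 non-responders; 10% not rolling over leaves 15.
- 35% response: 250 × 0.65 ≈ 162; 10% leaves 16.

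Early withdrawals who return for a follow-up PGA would add to these counts.

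**Step 2. What moves the median.** With m at risk and d first responses at Week 16, S(after Week 16) = S(Week 12) × (1 − d/m). The median is reached if d/m ≥ 1 − 0.5/S(Week 12).

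| S(Week 12) | Share needed | Example |
|---|---|---|
| 0.60 | 1 − 0.5/0.60 = 16.7% | 2 of 15: 0.60 × 13/15 = 0.52, not reached; 3 of 15: 0.60 × 12/15 = 0.48, reached |
| 0.65 | 1 − 0.5/0.65 = 23.1% | 3 of 16: 0.65 × 13/16 = 0.53, not reached; 4 of 16: 0.65 × 12/16 = 0.49, reached |
| 0.85 (vehicle, 15%) | 41.2% | rarely met |
| 0.80 (vehicle, 20%) | 37.5% | rarely met |

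**Step 3. How often.** The simulation used scheduled visit weeks, 25% dropout, 90% roll-over, and first responses spread 5/20/35/40% over Weeks 2/4/8/12 (assumed). Share of runs in which Week 16 sets the tapinarof median:

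| Week 16 first-response rate | 2% | 5% | 10% | 20% |
|---|---|---|---|---|
| 40% response | 2% | 7% | 23% | 59% |
| 35% response | 0.2% | 1.5% | 7% | 37% |

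At 40% response and a 10% Week 16 rate, varying roll-over from 60% to 95% moves the result from 13% to 27%. For vehicle at 90% roll-over it is at most about 2% for rates up to 10%, and 7% to 10% at a rate of 20%.

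**Step 4. Log-rank test.** Take 250 v 125 subjects, an assumed spread of 10/25/35/30%, and 15 v 11 at risk at Week 16. At 40% v 15%, z is 4.59 without Week 16, 4.71 with two tapinarof events there, and 4.31 with two vehicle events. At 35% v 20%, z is 3.00, then about 3.1 or 2.7. No conclusion changes.

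**Step 5. Does a Week 12 cut suffice?** Not on actual days, which is how SAP 12.7.3 counts. Visits fall on Day 85 ± 2, so non-responders seen on Day 83 are censored before responders seen on Day 87 are counted. Take 40% response with the 5/20/35/40% spread and visits even over the five days (assumed). The curve enters Week 12 at 0.76, and the share responding there is h = 0.16/0.76 = 0.2105. On actual days the curve ends at

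0.76 × (1 − h/5)(1 − h/4)(1 − h/3)(1 − h/2)(1 − h) = 0.76 × 0.596 = 0.45,

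against 0.76 × (1 − h) = 0.60 on scheduled weeks. Simulation gave 0.45 to 0.47, depending on the assumptions. The median can then be crossed inside the Week 12 window with no Week 16 data at all.

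**The case against.** The strongest reply is that Week 16 was never meant to count. SAP section 1 limits the plan to the double-blind phase, Protocol Table 1 puts Week 16 in a separate follow-up column, every other PGA, PASI and %BSA endpoint stops at Week 12, and where the SAP wants Week 16 (pruritus, DLQI, PSD, SF-36) it names it. This stands in part: inclusion follows from the literal wording and is not stated outright. But no sentence removes Week 16. SAP section 9 keeps Week 16 data as observed cases, SAP 11.4 defines a Week 16 window, and the SAP 12.8 table gives this endpoint no time limit. For adverse events, SAP 12.9.1 does say what counts for roll-over and other subjects; this endpoint has no such rule.

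A reader might also infer more than the documents support:
- *That the median will be about 16 weeks.* This needs particular off-drug response and roll-over rates, neither of which is given. At the planned 40%, two responses among 15 are not enough.
- *That the log-rank comparison is distorted.* Step 4 shows it barely moves.
- *That the late group is purely self-selected.* It also includes subjects who fail to qualify and premature withdrawals.
- *That everyone else is followed to Week 12.* Up to 25% may be lost before then.

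The planned Kaplan-Meier figure would show a late drop, which helps a careful reader but does not correct a reported median.

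**Conclusion.** The point holds in a limited form. On the literal rule, the curve after about Day 87 rests only on a small, non-random, off-drug group. Whether that group sets the tapinarof median is conditional. Cumulative response by Week 12 must be below 50% but not far below, as the planned 35% to 40% would give, and about one in six (at 0.60) to one in four (at 0.65) of those at risk must first respond at Week 16. If the curve has already crossed 0.5 by Week 12, Week 16 is irrelevant to the median. The counts of 15 and 16 rest on an assumed 90% roll-over.

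The endpoint is exploratory and outside the fixed testing sequence in SAP 11.6, so primary and secondary conclusions are untouched. This is a minor point that is worth closing because it is cheap to close.

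**What to change.** In SAP 12.7.3:
- Count only PGA assessments up to the Week 12 analysis visit, censor non-responders at their last PGA on or before that visit, and exclude Week 16.
- Measure time in scheduled visit weeks, or use an interval-censored method. With the cut alone, on actual days, the simulated curve still ended near 0.47 instead of 0.60 at 40% response.

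In SAP 12.8.2, show numbers at risk under the Kaplan-Meier figure.

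The cost is one or two sentences and no new data. At the planned rates the median may be reported as not reached in both arms, which is what 12 weeks of treatment data would support.

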#### 12.7.4 Functional Outcomes and Health-related Quality of Life Endpoints

To describe the effect of tapinarof cream, 1% on functional outcomes and the associated impact on daily activities and attitudes in adults with plaque psoriasis:

- Change in Peak Pruritus-Numeric Rating Scale (Peak Pruritus-NRS) from Baseline at Weeks 2, 4, 6, 8, 10, 12 and 16
- Change in psoriasis impact on daily activities, as measured by the Dermatology Life Quality Index (DLQI) total and individual dimension scores from Baseline at Weeks 4, 12, and 16

**The DLQI** is a 10-item PRO measure that assesses the extent to which the skin condition has affected the subject's quality of life over the past week, including 6 domains (daily activities, personal relationships, symptoms and feelings, leisure, work/school, and treatment). The total score (0-30) will be calculated as the sum of 10 questions with each ranging from 0 to 3. The scoring of each question is as follows:

Very much	Scored 3
A lot	Scored 2
A little	Scored 1
Not at all	Scored 0
Not relevant	Scored 0

Question unanswered	Scored 0
Question 7: “prevented work or studying”	Scored 3

If one question is left unanswered this is scored 0 and the scores are summed and expressed as usual out of a maximum of 30. If two or more questions are left unanswered the total DLQI score is missing. If question 7a is answered ‘yes’ or ‘not relevant’, then the answer of 7b will be ignored.

When summarizing the domain scores, if a domain contains two questions and the answer to one of the questions is missing, that domain will be scored as the answer to the non-missing question. If all the answers to questions in a domain are missing, the domain will not be scored.

- Change in psoriasis symptoms, as measured by the Psoriasis Symptom Diary (PSD), including total and 16 individual scores from Baseline at Weeks 2, 4, 8, 12, and 16.

PSD is a 16-item assessment measures self-reports of psoriasis symptoms, and impact on functional health. The total score will be calculated as the sum of 16 questions with each ranging from 0 to 10. If any of the 16 questions is unanswered, the total score will be considered as missing.

- Change in the eight domain scores, as measured by the RAND Short Form-36 (SF-36) questionnaire from Baseline at Weeks 4, 12, and 16.

The 8 domain scores below will be computed using the scoring rules for the RAND 36-Item Health Survey (Version 1.0):

- Physical functioning
- Role limitations due to physical health
- Role limitations due to emotional problems
- Energy/fatigue
- Emotional well-being
- Social functioning
- Pain
- General health

## 12.8 Efficacy Analyses

All efficacy outcomes will be analyzed in the ITT population. Only the primary and secondary efficacy endpoints will be analyzed in the PP population as supportive analyses, as summarized in the Table below.

Efficacy Endpoints	Primary	Sensitivity Analysis
--------------------	---------	----------------------

	Analysis	
Primary Endpoint 
 
PGA response at Week 12
 
	ITT, MI	ITT, OC ITT, TF ITT, LOCF PP, OC
Secondary Endpoints Categorical Endpoint: 
 
PASI-75 at Week 12
 
PGA 0 or 1 at Week 12
 
PASI-90 at Week 12
 
 Continuous Endpoint: 
 
Change in %BSA at Week 12
 
	ITT, MI	ITT, OC ITT, TF (categorical endpoint) ITT, LOCF PP, OC
Exploratory Endpoints 
 
Time to PGA response
 
	ITT, OC	N/A
Exploratory Endpoints 
 
PGA 0 or 1 at Weeks 2, 4, and 8
 
PGA response at Weeks 2, 4, and 8
 
Change in PASI from Baseline at Weeks 2, 4, 8, and 12
 
% change in PASI from Baseline at Weeks 2, 4, 8, and 12
 
PASI-50 at Weeks 2, 4, 8, and 12
 
PASI-75 at Weeks 2, 4, and 8
 
PASI-90 at Weeks 2, 4, and 8
 
Change in %BSA from Baseline at Weeks 2, 4, and 8
 
% change in %BSA from Baseline at Weeks 2, 4, 8, and 12
 
	ITT, MI	ITT, OC
Other Endpoints 
 
Change from Baseline in Peak NRS at Weeks 2, 4, 6, 8, 10, 12 and 16
 
% change from Baseline in Peak NRS at Weeks 2, 4, 6, 8, 10, 12 and 16
 
Peak NRS 4-point Responder at Weeks 2, 4, 6, 8, 10, 12 and 16
 
Change from Baseline in DLQI at Weeks 4, 12, and 16
 
% change from Baseline in DLQI Total Score at Weeks 4, 12 and 16
 
Change from Baseline in PSD at Weeks 2, 4, 8, 12, and 16
 
% change from Baseline in PSD Total Score at Weeks 2, 4, 8, 12 and 16
 
Change from Baseline in SF36 at Weeks 4, 12, and 16
 
	ITT, OC	N/A

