Investigator Assessed:										
PGA score ^m	X	X	X	X		X		X	X	X
%BSA affected ⁿ	X	X ^o	X	X		X		X	X	X
PASI		X	X	X		X		X	X	X
LTS ^p			X	X		X		X	X	X

Procedures and Assessment	Screening	Baseline	Double-Blind Vehicle-Controlled Treatment Phase						FU ^a	ET ^b
	V 1	V 2	V 3	V 4	P/C ^c	V 5	P/C ^c	V 6	V 7	NA
	Day -34 to Day -1	Day 1	Week 2 D 15 (±2 d)	Week 4 D 29 (±2 d)	Week 6 D 43 (±2 d)	Week 8 D 57 (±2 d)	Week 10 D 71 (±2 d)	Week 12 D 85 (±2 d)	Week 16 D 113 (±4 d)	NA
Completed by Subject:										
DLQI		X		X				X	X	X
SF-36		X		X				X	X	X
PSD		X	X	X		X		X	X	X
LTS			X	X		X		X	X	X
Peak Pruritus NRS ^q		X	X	X	X	X	X	X	X	X
Dispense/collect diary ^f		D	C/D	C/D		C/D		C		C
Review subject diaries for treatment compliance			X	X		X		X		X
Dispense (D)/Collect (C) study drug		D	C/D	C/D		C/D		C		C
Review instructions for study drug application ^s		X	X	X	X	X	X			
Study drug application under supervision ^t		X	X	X		X				
Enrollment (optional) in long-term study								X		

AE = adverse event (s); BMI = body mass index; BSA = body surface area; %BSA = percent of total BSA; D/d = day(s); DLQI = Dermatology Life Quality Index; ECG = electrocardiogram; eCRF = electronic Case Report Form; ET = early termination; FU = follow-up; HADS = Hospital Anxiety and Depression Scale; LTS = Local Tolerability Scale; NA = not applicable; NRS = Numeric Rating Scale; PASI = Psoriasis Area and Severity Index; P/C = phone contact; PGA = Physician Global Assessment; PK = Pharmacokinetics; PSD = Psoriasis Symptom Diary; SF-36 = 36-Item Short Form Survey; V = Visit; WOCBP = women of child-bearing potential.

^a The Follow-Up Visit will be performed for any subject who: (a) prematurely withdraws from the study, (b) fails to qualify for participation in the open-label long-term study, or (c) qualifies to participate in the open-label long-term study but elects not to enroll in that study.

^b Subjects who withdraw from the study before 12 weeks (Visit 6) will complete an Early Termination Visit.

^c Phone calls are scheduled between visits to assess AEs and concomitant medications, to review study drug application procedures, and to confirm subject's continued participation in the study. Subjects should be reminded to complete the diary and bring with them to the next clinic visit.

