## **3. STUDY DESIGN**

This is a double-blind, randomized, vehicle-controlled, Phase 3, multicenter study to evaluate the efficacy and safety of topical tapinarof cream, 1% compared with vehicle-control cream in adults with plaque psoriasis.

Following a 34-day screening period, eligible subjects will be randomized at a 2:1 ratio to receive once daily treatment with tapinarof cream, 1% or vehicle cream. Subjects will return to the clinic at Weeks 2, 4, 8, and 12 for efficacy and safety assessments. Additionally, subjects will be contacted by phone at Weeks 6 and 10 to assess adverse events (AEs) and concomitant medications, to review study drug administration instructions, and to confirm subject's continued participation in this study. Study drug will be dispensed to subjects during the clinic visits and will be administered at home between clinic visits as instructed by site personnel. Subjects will

be instructed to apply study drug once daily to all affected areas, including newly appearing lesions and lesions/areas that improve during the study. Subjects will apply sufficient study drug to cover completely each lesion with a thin layer of study drug and will record the time of study drug application in a daily diary provided by the study site. (Note that subjects are allowed, but not required, to treat fingernails, toenails, palms, soles, and scalp lesions with study drug; however, efficacy analyses will not include assessment of improvement of psoriasis in these areas.) Subjects will be instructed to maintain the dosing time chosen at the beginning of the study for their full study participation. At the phone contacts at Weeks 6, 10, and 14, subjects should be reminded to complete their daily diary and bring it with them to the next clinic visit.

At the end of 12 weeks of treatment in this study, subjects will have the option to enroll in a separate open-label long-term safety and efficacy study for an additional 40 weeks of treatment. Subjects who choose not to participate in the open-label long-term study, who fail to qualify for participation in the open-label long-term study, or who qualify to participate in the open-label long-term study but ultimately elect not to enroll in that study, will complete a Follow-up Visit approximately 4 weeks (Week 16 visit) after the end of treatment in this study. Subjects who withdraw from the study before Week 12 will complete an Early Termination Visit.

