### **12.8.3 Other Efficacy Analyses**

Change from baseline in DLQI, PSD, SF-36, and Peak Pruritus-NRS will be analyzed using an ANCOVA model with treatment as a main effect, baseline PGA score as a categorical covariate, and baseline value of the endpoint as a covariate. Percent change from baseline in DLQI, PSD and Peak Pruritus-NRS will be summarized and analyzed using the same method.

In addition, the proportion of subjects with at least a 4-point reduction from baseline in the Peak Pruritus-NRS among subjects with a baseline NRS score  $\geq 4$  will be summarized and analyzed following the same method as the dichotomized secondary endpoints. A plot will be used to illustrate this information.

Subject itch diary and in-clinic itch score assessments will be listed and summarized using descriptive statistics by day. If a subject completed diary itch score on the date of in-clinic visit, the itch score assessed in-clinic will be used in the summary. Change from baseline, treatment difference (Tapinarof cream 1% – Vehicle Cream) in mean change from baseline values and its associated 95% CI will be summarized by day. In addition, the treatment difference and its associated 95% CI will be plotted by day.

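### Week 16 arm comparisons of itch and quality of life use an off-treatment subset formed after randomisation and should be descriptive only

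*SAP*

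**What the plan says.** **What is analysed.** The last row of the table in SAP 12.8 covers itch ("Change from Baseline in Peak NRS at Weeks 2, 4, 6, 8, 10, 12 and 16", with percent change and a 4-point responder), DLQI ("Change from Baseline in DLQI at Weeks 4, 12, and 16"), PSD and SF-36. The analysis is given as ITT with observed cases, and no sensitivity analysis is planned. SAP 12.7.4 lists the same visits.

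**How.** SAP 12.8.3 states: "Change from baseline in DLQI, PSD, SF-36, and Peak Pruritus-NRS will be analyzed using an ANCOVA model with treatment as a main effect". The other terms are baseline PGA and the baseline value of the endpoint. Percent change is handled the same way where planned, and the itch responder follows the stratified CMH method of the dichotomised secondary endpoints. No visit is set aside. SAP 11.1 adds: "All statistical tests will be performed at the 0.05 (two-sided) level of significance". SAP 9 leaves Week 16 unimputed.

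**Who has Week 16 data.** Protocol 7.4 says: "Subjects who do not enroll in the open-label long-term study will return to the study site at Week 16". Footnote a of the Schedule of Assessments gives the visit to any subject who "a) prematurely withdraws from the study, (b) fails to qualify for participation in the open-label long-term study", or who qualifies but elects not to enrol. SAP 11.4 also assigns early-termination and unscheduled visits to Week 16 when they fall after the later of Day 87 and three days past last treatment.

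**When the subset forms.** SAP 3 states: "At the end of 12 weeks of treatment in this study, subjects will have the option to enroll in a separate open-label" study.

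**The concern.** Membership of the Week 16 set is settled after randomisation and, for most subjects, after 12 weeks of treatment. By then the design expects the arms to differ in response. If staying out of the open-label study, or withdrawing early, is related to how a subject is doing, the two arms' Week 16 remainders differ in prognosis. Adjusting for baseline PGA and baseline score does not remove that difference.

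The subjects are also about four weeks off treatment, so the contrast is not the on-treatment one reported at Week 12. At stake is a set of treatment differences, confidence intervals and p-values printed beside the Week 12 results under a label that suggests all randomised subjects.

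**Working it through.** **1. Inputs from the documents.** Allocation is 333 to 167, Week 12 response 40% versus 15%, and tests are two-sided at 0.05 (SAP 7 and 11.1). The plan gives no Week 16 sample size, power or roll-over rate. Its power statement for the primary endpoint does reproduce to rounding. For 35% versus 20%, Fisher exact power is 93.8% and the pooled normal value 94.5%, against a stated figure above 94%. For 40% versus 15%, both exceed 99.9%.

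**2. Number of Week 16 comparisons.** Counting SAP 12.7.4 and 12.8:
- itch: 3
- DLQI: total, 6 dimensions, percent change = 8
- PSD: total, 16 items, percent change = 18
- SF-36: 8 domains

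That is up to 3 + 8 + 18 + 8 = 37.

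**3. Model for the bias (assumed).** There is no true treatment effect at Week 16. Prognosis U is standard normal in both arms, and a subject responds at Week 12 if U exceeds the cut-off giving 40% or 15%. Week 16 change is −ρU − 0.3 × baseline + error, with ρ = 0.5 unless stated. Non-roll-over probability depends on Week 12 response. A positive bias makes tapinarof look worse.

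**4. One case by hand** (responders 10%, non-responders 30%, both arms). With φ the normal density at the cut-off, mean U is φ/p in responders and −φ/(1−p) in non-responders.
- Tapinarof: φ = 0.386, giving 0.966 and −0.644. Fraction not rolling over = 0.40×0.10 + 0.60×0.30 = 0.22, so n = 73. Responders' share = 0.04/0.22 = 0.182. Mean U = 0.182×0.966 − 0.818×0.644 = −0.351.
- Vehicle: φ = 0.233, giving 1.554 and −0.274. Fraction = 0.15×0.10 + 0.85×0.30 = 0.27, so n = 45. Responders' share = 0.015/0.27 = 0.056. Mean U = 0.056×1.554 − 0.944×0.274 = −0.173 (unrounded inputs).
- Bias = −0.5 × (−0.351 + 0.173) = +0.09 SD.

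**5. Simulation** (ANCOVA on treatment and baseline, 4000 runs per scenario).

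| Not rolling over: responders / non-responders | n, tapinarof/vehicle | Bias by formula (SD) | Bias simulated (SD) | Type I error |
|---|---|---|---|---|
| Everyone seen | 333/167 | 0 | 0.00 | 5.2% |
| At random, 5% to 40% | 17/8 to 133/67 | 0 | about 0 | about 5% |
| 5% / 15%, both arms | 37/23 | 0.09 | 0.09 | 5.5% |
| 30% / 10%, both arms | 60/22 | −0.04 | −0.03 | 5.6% |
| 10% / 30%, both arms | 73/45 | 0.09 | 0.10 | 8.2% |
| 5% / 30%, both arms | 67/44 | 0.13 | 0.13 | 10.5% |
| 10% / 30%, both arms, ρ = 0.7 | 73/45 | 0.13 | 0.13 | 11.1% |
| Tapinarof 5% / 30%, vehicle 30% / 30% | 66/50 | 0.24 | 0.25 | 25.8% |

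**6. The same problem on the DLQI scale (assumed).** Week 12 improvement is N(6, 5) versus N(3.5, 5), and Week 16 is 0.7 times Week 12 plus N(0, 3.5) noise. The true Week 16 difference is therefore 0.7 × (6 − 3.5) = 1.75 points. Roll-over is logistic, with intercept 2 at 5 points of improvement and slope ±0.2 per point, which leaves 12% to 19% not rolling over. Differences in raw arm means among those left:
- same slope in both arms: about 1.5
- good responders on tapinarof and poor responders on vehicle roll over: −3.7
- the reverse: +6.7

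**The case against.** The case against concerns size and consequence, and much of it stands.

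- **Dependence on response or arm is not documented.** Protocol 5.3 blinds subjects, investigators and sponsor, so the prospect of active drug does not by itself create opposite patterns by arm. Arm can act through response or tolerability, but the documents give neither a roll-over rate nor the long-term study's entry criteria.
- **A reader might infer that the Week 16 difference mostly reflects who left, or that its sign will reverse.** The documents do not support that. With the same pattern in both arms the DLQI example gives about 1.5 against 1.75, a shift of 0.25 points. The standard error at 12% to 19% remaining (about 40/20 to 63/32 subjects) is about 1.1 to 1.35 points. The −3.7 and +6.7 figures are assumed extremes that need opposite selection by arm, and they come from raw means rather than the planned ANCOVA.
- **The departure from the protocol is narrow.** Protocol 10.4.4 stops only the itch endpoint at Week 12. DLQI, PSD and SF-36 are to be followed over time, with ANCOVA specified there too.
- **Incompleteness is disclosed.** The table label includes observed cases, and SAP 9 says Week 16 is not imputed. That tells the reader data are missing, but not that the subset is selected.
- **Consequence is low.** These outcomes are outside the fixed sequence in SAP 11.6.

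None of this turns the planned test into a randomised comparison. The SAP's handling of the investigator-assessed scales points the same way: PGA, PASI and %BSA are also collected at Week 16, yet every planned arm comparison of them ends by Week 12.

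**Conclusion.** The point holds in this form. As written, the SAP produces Week 16 treatment comparisons ("will be analyzed using an ANCOVA model with treatment as a main effect, baseline PGA score as a categorical covariate") on an off-treatment subset formed after randomisation, and nothing in the model accounts for how it was formed. The comparison is unbiased only if membership is unrelated to outcome.

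Size and direction cannot be fixed from the documents. Under the assumed scenarios with no true effect, bias ran from −0.03 to 0.25 SD. Type I error was 5.5% to 11% with the same response-related pattern in both arms and about 26% in the arm-specific scenario. It stayed near 5% when non-roll-over was random. Primary and secondary conclusions are untouched. The change is still worth making, because the affected results would otherwise be read as ITT evidence and the correction is almost free.

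**What to change.** - In SAP 12.7.4, 12.8 and 12.8.3, limit ANCOVA and CMH comparisons to visits up to Week 12.
- Apply the same limit to the by-day itch treatment difference, its confidence interval and its plot. SAP 12.8.3 sets no end day, so the Week 16 clinic score would otherwise enter.
- Summarise Week 16 descriptively by arm, labelled 'off-treatment, subjects not entering the open-label study (including early withdrawals)'. Show the number of subjects and their baseline and Week 12 status by arm.
- List the added Week 16 itch time point in SAP 13, which at present reports no change other than the SF-36 scoring and the COVID-19 additions.
- Reconcile footnote a of the Schedule of Assessments with Protocol 3.1 and 7.4 on whether early withdrawals attend the Week 16 visit.

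The cost is SAP wording and fewer tests to program. The downside is that no formal Week 16 comparison is reported.
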